9.2.2 Oral Health Impact Profile

Patients will complete the 14-item Oral Health Impact Profile (OHIP-14) instrument at baseline and at the end of treatment³⁵. This is a validated instrument that assesses various aspects of oral health and function that has been shown to perform well in patients with oral mucosal diseases, including Oral Inflammatory Ulcerative Diseases³⁶.

9.2.3 Patient Reported Outcomes

Subjective assessments of subjects' oral symptoms will be obtained by using instruments from the NIH consensus documents for oral cGVHD, a condition that is very similar to other Oral Inflammatory Ulcerative Diseases (see Appendix 3 &4). These include report of mouth sensitivity at rest and sensitivity with stimulation (e.g. eating) on an eleven point scale. For the primary endpoint the worst sensitivity in the past week will be used. The clinician seeing the subject will

complete these forms at each study visit. Patients will also report daily sensitivity on an eleven point scale (see Appendix 2). Tolerability and compliance will also be evaluated, and a patient reported global assessment of overall improvement will be evaluated at the four-week visit.

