8.2 Blinding

This is an open label trial with no blinding.

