9.2 Study procedures

Potentially eligible subjects will be screened by one of the investigators by asking patients to rate their worst oral pain or pain score (0-10) over the previous week on a VAS. Those answering with at least a score of “7” (1/10) and that meet all other eligibility requirements (see Section 6) will be eligible for enrollment. All patients will sign informed consent for study participation. Each study visit is anticipated to take approximately 45 minutes. A urine pregnancy test will be performed for women of child bearing potential.

There is no financial compensation for participating in this study. Treatment will be administered on an outpatient basis. Study medication will be prescribed by authorized study staff physicians and filled by the Investigational Pharmacy at no expense for the patient. No investigational or commercial agents or therapies other than those described below may be administered with the intent to treat the participant’s Oral Inflammatory Ulcerative Diseases.

Subjects will be evaluated clinically at baseline before starting treatment and at the end of the four-week period, for a total of two visits. Comprehensive subjective and objective data will be collected (Appendix 3 & 4) and intraoral photographs will be obtained. Oral mucosal disease will be evaluated using both patient reported (questions/visual analog scales) and clinician assessed measures.

Subjects will be prescribed compounded dexamethasone 0.5mg/5ml solution in Mucolox™ (ARM A) or commercial dexamethasone 0.5mg/5ml solution only (ARM B). All subjects will also receive a prescription for fluconazole 200 mg tablets once-a-week as prophylactic antifungal therapy. Any subjects that are already taking an antifungal oral medication at the time of the study enrollment will continue their prescribed medication and will not need to take the additional weekly fluconazole dose. Subjects will return for evaluation after four weeks at which time the study endpoints will be assessed.

If there is worsening of Oral Inflammatory Ulcerative Diseases that requires initiation of new immunomodulatory medications (systemic or topical), patients will remain on treatment, but will be regarded as unevaluable for the primary endpoint.

	Day 1 (baseline)	Day 28 ± 5 days (end of study)
Clinical examination	x	x
OHIP-14	x	x
Patient Reported Outcomes	x	x

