9.3 Study Agents Administration

The Investigator or co-investigators will prescribe the study drug in the clinic and instruct the patient on study drug use. Both dexamethasone compounded 0.5mg/5ml solution in Mucolox™ and commercial dexamethasone solution will be dosed topically at a concentration of 0.5 mg/5mL.

A four week supply will be dispensed. The treatment instructions will be to rinse and spit (NOT swallow) with one teaspoon (5 mL) of the solution, three times a day for 5 minutes at a time, and not to eat or drink for 15 minutes afterwards. Subjects will maintain a diary (Appendix 2) and record each dose, the length of time rinsing, and any adverse effects.

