Appendix 1**INSTRUCTIONS FOR PREPARING & USING YOUR
TOPICAL SOLUTION****WHAT YOU WILL RECEIVE**

- One 480 mL bottle of concentrated solution (5 mg/5 mL)
- 4 tablets of fluconazole 200 mg

USING YOUR SOLUTION

You will be rinsing with your solution **3 times per day**.

1. Gently shake the bottle of solution.
2. Pour 5 mL of solution into the dosing cups provided.
3. Swish the solution in your mouth for 5 minutes, then spit – DO NOT SWALLOW!
4. Do not eat or drink for 15 minutes after rinsing.

Please take one table of fluconazole once a week

CONFIDENTIAL

This document is confidential. Do not disclose or use except as authorized.

	11													
	12													
	13													
	14													

	3													
	15													
	16													
	17													
	18													
	19													
	20													
	21													
	22													
	4													

CONFIDENTIAL

This document is confidential. Do not disclose or use except as authorized.

	23																						
	24																						
	25																						
	26																						
	27																						
	28																						

CONFIDENTIAL

This document is confidential. Do not disclose or use except as authorized.

Appendix 3

DEXAMETHASONE RINSE IN MUCOLOX™ FOR THE TREATMENT OF ORAL INFLAMMATORY ULCERATIVE DISEASES

VISIT #1

Subject Name _____

[figure not shown]
[figure not shown]
Medical Record Number _____

Date of Visit _____

SUBJECTIVE DATA (Over last two weeks unless specified)

MUCOSAL PATHOLOGY

- 1. Does your mouth hurt now? Y/N
- 2. Does it hurt to swallow food or drink? Y/N
- 3. How would you rate your worst mouth sensitivity over the last week?

No sensitivity

Worst sensitivity

CONFIDENTIAL

This document is confidential. Do not disclose or use except as authorized.

[figure not shown]
[figure not shown]
4. Do you avoid any foods because they make your mouth hurt?

- 0 = Not at all
- 1 = Slightly
- 2 = Moderately
- 3 = Quite a bit
- 4 = Extremely

If “yes”, what types of foods?

- a. Spicy foods
- b. Acidic foods
- c. Salty foods
- d. Hard/crunchy/crusty foods
- e. Other:

5. Do you feel that your oral intake (what you eat) is limited by your oral condition? Y/N

Not limited at all

Severely limited

Score: _____

If “Yes”, how limited do you feel it is?

- a. Partial limitation
- b. Severe limitation

6. Have you been bothered by ulcers in the mouth?

- 0 = Not at all
- 1 = Slightly
- 2 = Moderately
- 3 = Quite a bit
- 4 = Extremely

CONFIDENTIAL

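### Section 9.2.3 has the unblinded clinician complete the visit forms that hold the primary sensitivity item, and nothing says the patient marks it: an avoidable risk of interviewer or recording bias

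*Combined protocol and SAP*

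**What the plan says.** Section 9.2.3 of the protocol, on patient-reported outcomes, names the primary item: "For the primary endpoint the worst sensitivity in the past week will be used". It then assigns the paperwork, in a sentence that runs across a page break: "The clinician seeing the subject will" "complete these forms at each study visit". The forms are those of Appendices 3 and 4. Item 3 on each is put to the patient ("How would you rate your worst mouth sensitivity over the last week"), and the same forms carry the REU grid and the photograph check.

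On blinding, section 8.2 is brief: "This is an open label trial with no blinding". No independent or masked assessor is described elsewhere. Section 9.3 adds that "The Investigator or co-investigators will prescribe the study drug in the clinic".

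Two other self-reported measures are handled differently. Section 9.2.2 states: "Patients will complete the 14-item Oral Health Impact Profile (OHIP-14) instrument at baseline and at the end of treatment". Section 9.2.3 itself has patients report sensitivity each day on an eleven-point scale, in the Appendix 2 diary.

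**The concern.** A patient-reported score is best protected when the patient alone produces the mark. If a clinician who knows the arm asks the question and writes down the number, the tone of the question, a follow-up prompt or the rounding of a hesitant answer can differ by arm. Background section 1.1.3 reports that the group's own pilot favoured the Mucolox arm on REU score, so study clinicians may hold an expectation. Section 5.3 has the evaluating physicians review the diaries at the four-week visit, and the plan does not say whether item 3 is scored before or after that review.

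A shift common to both arms cancels in the between-arm comparison. A shift that differs by arm goes straight into the estimated treatment effect, and neither the t-test nor the Mann-Whitney test of section 13.1.1 can separate it from a drug effect.

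Open-label bias is often accepted because blinding or an independent assessor costs resources. That defence does not cover this component, because self-completion needs neither.

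**Working it through.** **Who produces each self-reported score**

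| Measure | Who completes it | Section |
|---|---|---|
| Worst sensitivity, past week (primary, item 3) | Clinician seeing the subject completes the form; who marks the scale is not stated | 9.2.3, Appendices 3 and 4 |
| OHIP-14 (secondary) | Patient | 9.2.2 |
| Daily sensitivity (listed with the primary endpoint in 5.1) | Patient, in the diary | 9.2.3, Appendix 2 |

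Of these three, the visit score that defines the main primary comparison is the only one on a form assigned to the clinician. The protocol gives no reason.

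**Inputs for the illustration (section 13.2)**

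- SD of change 1.4 in each arm, target difference 2.0, two-sided alpha 0.05, at least 80% power.
- 15 per arm with 5% loss: 15 × 0.95 = 14.25, taken as 14 evaluable.
- Assumed, not in the documents: a between-arm shift b in recorded change of 0.25, 0.5 or 1.0 point, and no true difference.

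**The plan's own figure.** For a difference of 2.0 and SD 1.4, the two-sample t-test needs 8.76, so 9 per arm, for 80% power, or 10 after 5% loss. The stated 15 is not reproduced at 80%. It does match 95% power (13.8, so 14, then 15 after loss). Power is 95.3% with 14 per arm and 96.5% with 15, so the stated minimum is met and the discrepancy is on the safe side. The present point does not depend on it.

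**Effect of a shift**

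SE = 1.4 × √(2/14) = 0.529, with df = 2 × 14 − 2 = 26. The noncentrality is b / SE, and the rejection rate is the probability that a noncentral t with 26 df falls outside the two-sided 5% limits.

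| Assumed shift b | b / 0.529 | Rejection rate, 14 per arm | Rejection rate, 15 per arm |
|---|---|---|---|
| 0 | 0 | 5.0% | 5.0% |
| 0.25 | 0.47 | 7.4% | 7.6% |
| 0.5 | 0.94 | 14.9% | 15.7% |
| 1.0 | 1.89 | 44.4% | 47.2% |

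The inflation depends on the SD. With an assumed SD of 2.0 and 14 per arm, SE = 2.0 × √(2/14) = 0.756 and the rates are 6.2%, 9.8% and 24.7%.

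On the scale of the target effect, 0.5 / 2.0 is one quarter and 1.0 / 2.0 is one half.

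**What this does not show.** The formula takes any differential shift, whatever its source. It does not isolate the interviewer or recording part, and nothing in the documents allows the total to be divided between clinician and patient.

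**The case against.** The strongest reply is that completing the forms may mean no more than filling in a case report form packet. The packet includes the REU grid, which a clinician must complete, and section 14.1 has study personnel transfer source data to the paper CRF. Item 3 is worded as the patient's own rating between two anchors, and section 9.2 classes these scales as patient reported: "Oral mucosal disease will be evaluated using both patient reported (questions/visual analog scales) and clinician assessed measures". A reader might infer that the clinician scores in the patient's place. The documents do not support that. They support only that the mode of administration is left open on a form assigned to the clinician. At screening, investigators ask for the score (sections 6.1 and 9.2), so an interview at the endpoint visits is plausible, but it is not stated.

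A reader might also infer that the person completing the form is the treating or prescribing clinician. Section 9.2.3 says only that it is the clinician seeing the subject. Section 9.3 makes an overlap with the prescriber likely but does not establish it. With no blinding, the concern does not need that step.

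The daily diary is a partial safeguard. Its last week offers a patient-recorded check on item 3, and changes in the daily score are listed with the primary endpoint. This softens the consequence, but the diary does not replace item 3 as the score used for the primary change.

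Finally, the shifts are chosen rather than derived. At 0.25 point the inflation is modest, and the 44% figure needs a shift of half the target effect. That stands, and it is why the figures are offered only as an illustration.

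**Conclusion.** The point holds as a risk that is cheap to remove, not as a demonstrated bias. It rests on four facts in the text: the primary item is on a form assigned to the clinician; that clinician is not blinded; no passage says the patient marks the item; and the protocol already relies on self-completion for two other measures.

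The size cannot be taken from the documents. Under the section 13.2 SD of 1.4, 14 per arm and no true difference, a differential shift of 0.25 to 1.0 point from any source would raise the false-positive rate from 5% to between about 7% and 44%. A larger SD would make it smaller. It would be wrong to read these rates as the error caused by clinician recording, or as what the fix would recover: the fix removes one source, and the patient's own expectation in an open-label trial is untouched.

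**What to change.** Amend section 9.2.3 so that at both visits the patient marks item 3 and the other subjective items alone on paper, before seeing the clinician and before the diary is reviewed. The OHIP-14 is already patient-completed; have it done in the same sitting. The clinician then completes only the REU grid and photographs, checks the patient pages for blanks, and neither prompts nor alters an answer. Split the Appendix 3 and 4 forms into patient and clinician pages to match.

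The cost is one amended sentence, a re-paginated paper form and a brief check at each visit for items left blank. It needs no extra staff, visits or patients, and changes no sample-size figure or treatment. If the intention was always that the patient marks the scale, the amendment simply puts that on record.

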9.2.4 Treatment Regimen

A four week supply of compounded dexamethasone 0.5mg/5ml solution in Mucolox™ (Arm A) and dexamethasone 0.5mg/5ml solution (Arm B) will be dispensed. The treatment instructions will be to rinse and spit (NOT swallow) with one teaspoon (5 mL) of solution, three times a day for 5 minutes at a time, and not to eat or drink for 15 minutes afterwards. Subjects will maintain a diary (Appendix 2) and record each dose, the length of time rinsing, and any adverse effects (e.g. transient burning).

Regimen Description						
	Agent	Premedications; Precautions*	Dose	Route	Schedule	Cycle Length
Arm A	Dexamethasone in Mucolox™	None	5mL x 0.1mg/mL = 0.5 mg/rinse, 3 times/day =1.5 mg	Oral Rinse, 5 mins. each time (do not swallow)	7 days/week	28 days (4 weeks) One Cycle Only*
Arm B (standard of care)	Dexamethasone solution	None	5mL x 0.1mg/mL = 0.5 mg/rinse, 3 times/day =1.5 mg	Oral Rinse, 5 mins. each time (do not swallow)	7 days/week	28 days (4 weeks) One Cycle Only*

*All subjects will be treated with fluconazole 200 mg once-a-week dosing for prophylaxis (see section 5.5)

9.3 Study Agents Administration

The Investigator or co-investigators will prescribe the study drug in the clinic and instruct the patient on study drug use. Both dexamethasone compounded 0.5mg/5ml solution in Mucolox™ and commercial dexamethasone solution will be dosed topically at a concentration of 0.5 mg/5mL.

A four week supply will be dispensed. The treatment instructions will be to rinse and spit (NOT swallow) with one teaspoon (5 mL) of the solution, three times a day for 5 minutes at a time, and not to eat or drink for 15 minutes afterwards. Subjects will maintain a diary (Appendix 2) and record each dose, the length of time rinsing, and any adverse effects.

9.3.1 Adverse Events

Information regarding occurrence of adverse events will be captured throughout the study. Duration (start and stop dates and times), severity/grade, outcome, treatment and relation to study drug will be recorded on the case report form (CRF). The PI or covering clinician will determine whether an adverse event was expected and/or related to study procedures. Study subjects will be asked to report any adverse events or concerns to study staff as they arise.

9.3.2 Pregnancy Test

A urine pregnancy test will be obtained from female subjects who are of childbearing age prior to their participation in the study.

10 ADVERSE EXPERIENCE REPORTING AND DOCUMENTATION

10.1 Adverse Events

An adverse event (AE) is any untoward medical occurrence in a clinical investigation of a patient administered a pharmaceutical product and that does not necessarily have a causal relationship with the treatment. An AE is therefore any unfavorable and unintended sign (including an abnormal laboratory finding), symptom or disease temporally associated with the administration of an investigational product, whether or not related to that investigational product. An unexpected AE is one of a type not identified in nature, severity, or frequency in the current Investigator's Brochure or of greater severity or frequency than expected based on the information in the Investigator's Brochure.

The Investigator will probe, via discussion with the subject, for the occurrence of AEs during each subject visit and record the information in the site's source documents. Adverse events will be recorded in the patient CRF. Adverse events will be described by duration (start and stop dates and times), severity, outcome, treatment and relation to study drug, or if unrelated, the cause.

AE Severity

The National Cancer Institute's Common Terminology Criteria for Adverse Events (CTCAE) Version 3.0 should be used to assess and grade AE severity, including laboratory abnormalities judged to be clinically significant. The modified criteria can be found in the study manual. If the experience is not covered in the modified criteria, the guidelines shown in Table 1 below should be used to grade severity. It should be pointed out that the term "severe" is a measure of intensity and that a severe AE is not necessarily serious.

Table 1. AE Severity Grading

Severity (Toxicity Grade)	Description
Mild (1)	Transient or mild discomfort; no limitation in activity; no medical intervention or therapy required. The subject may be aware of the sign or symptom but tolerates it reasonably well.
Moderate (2)	Mild to moderate limitation in activity, no or minimal medical intervention/therapy required.
Severe (3)	Marked limitation in activity, medical intervention/therapy required, hospitalizations possible.
Life-threatening (4)	The subject is at risk of death due to the adverse experience as it occurred. This does not refer to an experience that hypothetically might have caused death if it were more severe.

AE Relationship to Study Drug

The relationship of an AE to the study drug should be assessed using the following the guidelines in Table 2.

Table 2. AE Relationship to Study Drug

Relationship to Drug	Comment
Definitely	Previously known toxicity of agent; or an event that follows a reasonable temporal sequence from administration of the drug; that follows a known or expected response pattern to the suspected drug; that is confirmed by stopping or reducing the dosage of the drug; and that is not explained by any other reasonable hypothesis.
Probably	An event that follows a reasonable temporal sequence from administration of the drug; that follows a known or expected response pattern to the suspected drug; that is confirmed by stopping or reducing the dosage of the drug; and that is unlikely to be explained by the known characteristics of the subject's clinical state or by other interventions.
Possibly	An event that follows a reasonable temporal sequence from administration of the drug; that follows a known or expected response pattern to that suspected drug; but that could readily have been produced by a number of other factors.
Unrelated	An event that can be determined with certainty to have no relationship to the study drug.

10.2 Serious Adverse Experiences (SAE)

An SAE is defined as any AE occurring at any dose that results in any of the following outcomes:

1. death
2. a life-threatening adverse experience
3. inpatient hospitalization or prolongation of existing hospitalization
4. a persistent or significant disability/incapacity
5. a congenital anomaly/birth defect

Other important medical events may also be considered an SAE when, based on appropriate medical judgment, they jeopardize the subject or require intervention to prevent one of the outcomes listed.

10.2.1 Serious Adverse Experience Reporting

Study sites will document all SAEs that occur (whether or not related to study drug) per [UCSF CHR Guidelines](#). The collection period for all SAEs will begin after informed consent is obtained and end after procedures for the final study visit have been completed.

In accordance with the standard operating procedures and policies of the local Institutional Review Board (IRB)/Independent Ethics Committee (IEC), the site investigator will report SAEs to the IRB/IEC.

11 DISCONTINUATION AND REPLACEMENT OF SUBJECTS

11.1 Early Discontinuation of Study Drug

A subject may be discontinued from study treatment at any time if the subject, the investigator, or the Sponsor feels that it is not in the subject's best interest to continue. The following is a list of possible reasons for study treatment discontinuation:

- Subject withdrawal of consent (or assent)
- Subject is not compliant with study procedures
- Adverse event that in the opinion of the investigator would be in the best interest of the subject to discontinue study treatment
- Protocol violation requiring discontinuation of study treatment
- Lost to follow-up
- Sponsor request for early termination of study
- Positive pregnancy test (females)

If a subject is withdrawn from treatment due to an adverse event, the subject will be followed and treated by the Investigator until the abnormal parameter or symptom has resolved or stabilized.

All subjects who discontinue study treatment should come in for an early discontinuation visit as soon as possible and then should be encouraged to complete all remaining scheduled visits and procedures.

All subjects are free to withdraw from participation at any time, for any reason, specified or unspecified, and without prejudice.

Reasonable attempts will be made by the investigator to provide a reason for subject withdrawals. The reason for the subject's withdrawal from the study will be specified in the subject's source documents (see below for early termination procedures).

12.3 Withdrawal of Subjects from the Study

A subject may be withdrawn from the study at any time if the subject, the investigator, or the Sponsor feels that it is not in the subject's best interest to continue.

All subjects are free to withdraw from participation at any time, for any reason, specified or unspecified, and without prejudice.

Reasonable attempts will be made by the investigator to provide a reason for subject withdrawals. The reason for the subject's withdrawal from the study will be specified in the subject's source documents. As noted above, subjects who discontinue study treatment early (i.e., they withdraw prior to Visit 2) should have an early discontinuation visit. Subjects who withdraw after Visit 1 but prior to Visit 2 should be encouraged to come in for a final visit (and the procedures to be followed would include those for their next scheduled visit).

